##### 4.6.2 Secondary outcomes

The secondary outcomes are:

- changes in skill grade and associated change in wage
- adherence with spectacle wear
- change in attitude towards eye health, glasses wear and uptake of eyecare services
- Visual Function using the APEDS Visual Function Questionnaire
- intervention cost-benefit analysis

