##### **4.10.2 Data collection during trial**

Daily efficiency data for each employee in the sewing department will be collected routinely by a productivity measurement system executed by the GBL team using a PushButton counter device. Wage and employment status data will be collected on a monthly basis from Shahi's Human Resource division. These data will be assessed at the end of the 3-month intervention period. Intervention costs will be collected by VisionSpring and assessed at the end of the 3-month intervention period. Secondary outcome data will be collected using the following data collection forms

- Baseline Assessment (following eye examination)
- Endline Assessment (at the end of the 3-month intervention period)
- Spectacle Wear Compliance (on a weekly basis over the 3-month intervention period)

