### **6. ADHERENCE TO THE INTERVENTION**

Adherence to the intervention will be assessed through observation of spectacle wear while working. Adherence will be measured surreptitiously on a daily basis. The enumerators assessing spectacle wear compliance are GBL staff members familiar to Shahi workers but are not revealed to be collecting glasses wear adherence data to ensure minimum modification of compliance behaviour in present of enumerators.

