## 9. COMPARATIVE ANALYSES

### 9.1 Analysis of primary and secondary outcomes

The primary endpoint is difference in efficiency during the 3 months of intervention between the treatment and control groups. The objective is to show that glasses-wear is superior to non-wear in improving worker efficiency. The null-hypothesis will be rejected on a 5% level if the two-sided 95% CI of the treatment full analysis set difference  $\mu_{\text{glasses}} - \mu_{\text{non-glasses}}$  excludes 0. If the lower limit is above 0, superiority of glasses wear against non-wear can be concluded. The hypothesis will be tested using an analysis of covariance (ANCOVA) model. In the regression specification, the outcome variable will be daily mean efficiency for each participant per day. The factors, covariates and interaction terms in the ANCOVA model are listed in the table below.

Factors and covariates at baseline	Type	Categories
Randomised treatment	Factors	Intervention, Control
Sex	Factors	Male, Female
Skill grade	Factors	<median, $\geq$ median
Factory type	Factors	Urban, rural
Spectacle wear compliance	Factors	<median, $\geq$ median
Age	Covariate	Not applicable
Baseline efficiency	Covariate	Not applicable

The factors and covariates will be included in the model as main effects in an additive structure. The estimated treatment difference between glasses-wear and non-wear will be reported together with the associated two-sided 95% CI and corresponding p-value. The standard errors will be clustered at the individual participant level.

Linear regression analyses will be performed on potential determinants of primary and secondary outcomes. The study group and all significant variables with p values less than 0.20 in simple regression analyses will be included in multiple regression models. Histograms, normal quantile plots (QQ Plot), and the Shapiro-Wilk normality test will be used to test the normality assumption in regression models. For the APEDS VFQ tool, a composite score (16 items) will be created on 0-100 scales, with higher scores indicating better results. Intervention costs will comprise the screening test, glasses (and any replacement thereof) as well as direct and indirect costs to the company for facilitating workplace-based sight tests. We will report cost effectiveness distinguishing between study costs and program costs. The cost effectiveness analysis will include both the costs to identify presbyopia and treat presbyopia.

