The analysis of primary and secondary outcomes will be adjusted for the minimisation factors (age, work tenure at the textile factory, efficiency during baseline assessment) to account for the correlation between treatment groups introduced by balancing the randomisation. The analysis will incorporate adjustment for glasses wear adherence to

account for any potential confounding effect on the productivity measures. Adherence to wearing glasses will be considered a covariate in the regression models assessing primary and secondary outcomes. Both the crude unadjusted and adjusted estimates will be presented, but the primary inference will be based on the adjusted analysis.

For multiple imputation of missing data in assessing primary outcomes we will create 20 copies of the data, in which missing values shall be imputed by chained equations, and the datasets will be averaged.

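### Section 9.1 lets a p<0.20 screen over an unlisted pool add covariates to the group comparisons, and separately names post-randomisation adherence as a covariate, so the adjusted effect need not be the intention-to-treat effect

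*SAP*

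**What the plan says.** SAP 9.1 gives several instructions that bear on the same models.

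- **Fixed part.** All analyses are adjusted for three factors, in the sentence that begins "The analysis of primary and secondary outcomes will be adjusted for the minimisation factors (age, work tenure at the textile factory, efficiency during baseline assessment". These are the factors that define the strata in 4.9.
- **Screened part.** "Linear regression analyses will be performed on potential determinants of primary and secondary outcomes". Then: "The study group and all significant variables with p values less than 0.20 in simple regression analyses will be included in multiple regression models". There is no candidate list and no restriction to baseline measurements.
- **Adherence.** "Adherence to wearing glasses will be considered a covariate in the regression models assessing primary and secondary outcomes". Section 6 says when it is observed: "Adherence will be measured surreptitiously on a daily basis". Section 4.6.2 also lists "adherence with spectacle wear" as a secondary outcome.
- **Which estimate counts.** "Both the crude unadjusted and adjusted estimates will be presented, but the primary inference will be based on the adjusted analysis".

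The primary outcome has its own table of ANCOVA terms; no secondary outcome has one. That table is headed as baseline factors, yet it includes spectacle wear compliance. Section 7.1 promises intention to treat for all outcomes, and 9.3 sets 99% confidence intervals for secondary outcomes. The combined protocol and SAP has the same p<0.20 rule in its 9.1, but not the two sentences on adherence adjustment.

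**The concern.** In a randomised comparison, covariates should be named in advance and measured before treatment can change them. The screen secures neither. It picks covariates by their observed association with the outcome, so the model for each outcome cannot be written down before the data are seen.

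The second gap matters more. The trial collects a good deal after randomisation, for example "Wage and employment status data will be collected on a monthly basis" (4.10.2), as well as an endline assessment and spectacle-wear observations. A variable that glasses change, and that in turn affects the outcome, is the kind that passes a screen on association with the outcome. Once it sits beside study group, the group coefficient measures only what is left after part of the treatment effect has been removed. If the variable also shares an unmeasured cause with the outcome, the coefficient can be biased even when glasses do nothing.

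At stake is whether the adjusted estimate, which carries the inference, is the effect promised in 7.1.

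**Working it through.** **1. The plan's own figure.** Section 4.8 (difference 0.0425, SD 0.19, correlation 0.8, two-sided 5%, power 90%):

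n = 2 × (1.960 + 1.282)² × 0.19² × (1 − 0.8²) / 0.0425² = 420.0 × 0.36 = 151.2, rounded up to 152 per group.

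This reproduces, but it concerns the primary outcome. The documents give no effect size or power for any secondary outcome, so every effect below is an assumption.

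**2. Completers.** 250 per group with 10% monthly loss over three months: 250 × 0.9³ = 182.25, taken as 182 per arm, 364 in all.

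**3. How much the screen leaves open.** A pure-noise candidate passes with probability 0.20. With 10 such candidates, 10 × 0.20 = 2 enter on average, and the chance of at least one is 1 − 0.8¹⁰ = 0.89. In a simulation with 10 baseline candidates, three of them prognostic, about 130 different covariate sets were selected over 3,000 replicates.

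**4. Baseline candidates only.** Two simulations at N = 364, no true effect, two-sided 1% test:

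| Candidates | Replicates | Type I error | Monte Carlo SE at 1% |
|---|---|---|---|
| 13 noise | 8,000 | 0.008 | √(0.01 × 0.99 / 8,000) = 0.0011 |
| 10, three prognostic | 3,000 | 0.011 | √(0.01 × 0.99 / 3,000) = 0.0018 |

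Both are within two standard errors of nominal. The first gave 0.046 at the 5% level. In the second set-up, a true effect of 0.40 was estimated as 0.395. A baseline-only screen does almost no harm to bias or error rate.

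**5. One candidate that glasses affect.** Assume glasses shift a mediator by 0.5, the mediator acts on the outcome with slope 0.3, and the direct effect is 0.15. The residual SD is 1 for both. Total effect = 0.15 + 0.5 × 0.3 = 0.30.

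- *Mediator left out.* Within-group SD = √(1 + 0.3²) = 1.044. SE = 1.044 × 2/√364 = 0.109. z = 0.30/0.109 = 2.74. Power at 1% = Φ(2.74 − 2.576) = 0.57.
- *Mediator included.* The coefficient estimates 0.15. The variance inflation from its correlation with group is 1 + 0.5² × 0.25 = 1.0625, so SE = (2/√364) × √1.0625 = 0.108. z = 0.15/0.108 = 1.39. Power = Φ(1.39 − 2.576) = 0.12. Simulation of the screened model gave an estimate of 0.146 and power of 0.116.

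Other assumed values show the same pattern. For a true 0.40, a fixed baseline model gave 0.40 with power of about 0.90. With the screen open to one mediator, the estimate was 0.20 with power 0.28 (half mediated), or 0.08 with power 0.03 (80% mediated). The mediator passed the screen in about 100% of replicates.

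**6. No true effect, shared cause.** Assume group shifts the post-randomisation variable by 0.5 or 0.8, and an unmeasured cause acts on both it and the outcome with coefficient 0.5. Type I error at the 1% level was 0.047 and 0.122 for the screened model, against 0.011 and 0.006 for the fixed one. So the error is not always conservative.

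**7. Adherence, the covariate the SAP names.** Assume 80% wear in the intervention group (the figure in 4.8), 0% or 10% in control, and an effect of 0.40 acting wholly through wear.

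| Control wear | Group effect without adherence (SE) | With adherence (SE) |
|---|---|---|
| 0% | 0.399 (0.106) | −0.003 (0.182) |
| 10% | 0.398 (0.107) | 0.002 (0.148) |

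Under these assumptions adjustment removes the whole effect. Because 9.1 names adherence outright, it need not pass the screen. Where adherence is itself the outcome, a literal reading makes it its own covariate.

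**The case against.** The best defence has four parts.

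- *The secondary models already have a specified core.* This stands. A reader might infer that the screen is the only model-building rule for secondary outcomes. It is not: study group is always kept and three baseline factors are fixed. The screen decides only what is added.
- *The SAP does not say that post-randomisation variables will be screened.* This also stands. A reader might infer that monthly wage, later skill grade or endline attitudes will enter the models, but no section names them as candidates. The text is silent. Adherence is different: it is named, and it is observed after randomisation.
- *The two sentences may describe a separate determinants analysis.* That reading is possible. Against it, the rule forces study group in, stands in the section on comparing outcomes, and is not labelled exploratory. Section 11 keeps that status for analyses that are not specified.
- *The damage is limited.* In part it is. The threshold is mechanical, and crude estimates are shown beside the adjusted ones, so an unscreened comparison will always be visible. But the crude estimate does not carry the inference. It would be wrong to claim that selecting covariates by p-value itself invalidates the 99% intervals: with baseline candidates, the error rate stayed close to nominal.

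**Conclusion.** The point holds. Section 9.1 leaves the covariate set partly to the data, does not confine it to baseline variables, and names adherence as a covariate in the models that carry the inference. Secondary outcomes are more exposed because they have no listed model. For the primary outcome it is unclear whether the screen adds to the ANCOVA table or stands apart from it.

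The size depends on what enters. With baseline variables only, the defect is incomplete pre-specification and little more. With a variable that glasses affect, the group coefficient is no longer the intention-to-treat effect. The halved estimate and the fall in power from about 57% to 12% illustrate that mechanism under assumed effects. They are not forecasts for this trial, and they breach no stated target, since the plan sets no power for secondary outcomes. The near-zero adherence-adjusted effect likewise assumes that the benefit acts wholly through wear.

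This should be changed before unmasking.

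**What to change.** 1. Remove the p<0.20 screen from all between-group comparisons, primary and secondary.
2. For each secondary outcome compared between groups by regression, state one fixed model: study group, age, work tenure, baseline efficiency, the outcome's own baseline value where it was measured, and any further baseline covariates named before unmasking. The cost-benefit analysis need not be forced into this form.
3. Remove adherence from the intention-to-treat models for primary and secondary outcomes. Deleting the screen alone would leave the adherence sentences in force. Adherence would still be described under 8.4.
4. Keep the primary ANCOVA table to baseline variables, which means taking out spectacle wear compliance.
5. If a determinants analysis is wanted, label it exploratory and do not report its group coefficient as the treatment effect.

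The cost is SAP wording only; no new data are needed. What is lost is the standing of the multivariable determinants model, which becomes exploratory.

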## 8.2 Baseline comparability of randomised groups

Participants in randomised groups will be described separately with respect to the following characteristics at trial entry:

- age
- sex
- education level
- marital status
- number of children and dependants
- median wage compared to urban Bangalore and urban India
- visual function (APEDS VFQ tool)
- uncorrected visual acuity in each eye separately at distance and both eyes together at near
- mean power of near correction required
- baseline work productivity
- attitudes towards vision correction
- access to local eyecare services
- history of uptake of eyecare services

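### Optional free improvement, one secondary outcome: SAP 9.1 does not fix the baseline APEDS VFQ score as a covariate, although it is already collected

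*SAP*

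**What the plan says.** SAP 4.6.2 lists among the secondary outcomes "Visual Function using the APEDS Visual Function Questionnaire". The score is available before treatment: SAP 8.2 includes "visual function (APEDS VFQ tool" among the characteristics described at trial entry. SAP 4.10.2 collects secondary outcome data on two forms that matter here, "Baseline Assessment (following eye examination" and "Endline Assessment (at the end of the 3-month intervention period".

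SAP 9.1 gives the scoring: "For the APEDS VFQ tool, a composite score (16 items) will be created on 0-100 scales, with higher scores indicating better results". It does not say in terms whether the endline score or the change from baseline is compared.

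Four statements in 9.1 bear on the covariates:

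- The ANCOVA table is introduced for the efficiency hypothesis. Its only baseline outcome measure is baseline efficiency.
- For all outcomes: "The analysis of primary and secondary outcomes will be adjusted for the minimisation factors (age, work tenure at the textile factory", with baseline efficiency as the third factor.
- For all outcomes: "Adherence to wearing glasses will be considered a covariate in the regression models assessing primary and secondary outcomes".
- For regressions on potential determinants of the outcomes: "The study group and all significant variables with p values less than 0.20 in simple regression analyses will be included in multiple regression models". No candidate variables are named.

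The combined protocol and SAP names a different instrument (THRIVE) and likewise gives no baseline-score rule for it.

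**The concern.** The plan adjusts the primary outcome for its own baseline and takes credit for that in the sample size. For APEDS it fixes baseline efficiency, which is another outcome's baseline, and leaves out the baseline value of the score being analysed. That value will usually be the strongest single predictor of the endline score, and it is already in the database.

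Two things are at stake, both small. One is precision on a secondary outcome that SAP 9.3 reports with 99% intervals. The other is certainty: 9.1 bases inference on the adjusted analysis, and for APEDS the covariate set depends on whether someone offers the baseline score to a data-driven screen. Leaving the score out does not bias a randomised comparison.

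**Working it through.** **The plan's own figure.** No sample size, SD or correlation is given for APEDS. The one figure that can be reproduced is for efficiency (SAP 4.8): difference 0.0425, SD 0.19, two-sided 0.05, power 90%, serial correlation 0.8. The two-sample size is 421 per group, and 421 × (1 − 0.8²) = 421 × 0.36 = 151.6, so 152 per group. This agrees with the plan and is untouched by the present point. It shows that the plan already uses baseline adjustment for efficiency. The 0.8 belongs to efficiency and should not be carried over to APEDS.

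**Inputs for APEDS.**

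- r, the within-arm baseline-endline correlation left after the other fixed covariates: assumed 0.3, 0.5 or 0.7.
- Participants at endline: 500 × 0.9³ = 364, or about 182 per group (SAP 4.8: 500 randomised, 10% lost per month, 3 months).
- Confidence level: 99% (SAP 9.3).

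**Formulas.** With the variance of the endline-only difference set to 1, ANCOVA on the baseline score has variance 1 − r². A change score without the baseline covariate has variance 2(1 − r), assuming equal SDs at the two times. The CI ratio of ANCOVA to endline-only is √(1 − r²). The ratio of ANCOVA to change score is √((1 + r)/2).

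| r | ANCOVA / endline-only | Narrower by | ANCOVA / change score | Narrower by |
|---|---|---|---|---|
| 0.3 | 0.954 | 4.6% | 0.806 | 19.4% |
| 0.5 | 0.866 | 13.4% | 0.866 | 13.4% |
| 0.7 | 0.714 | 28.6% | 0.922 | 7.8% |

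In SD units, with 182 per group, the 99% half-width is 0.270 for endline-only. It is 0.257, 0.234 or 0.193 with ANCOVA.

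**If r is the raw correlation.** Suppose the other covariates together correlate 0.3 with both scores (assumption). The residual correlation is then (r − 0.09)/0.91 = 0.231, 0.451 or 0.670. The gain over endline-only becomes 2.7%, 10.7% or 25.8%, and over a change score 21.6%, 14.8% or 8.6%.

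**Does adherence in the model alter this?** A simulation used 364 participants and 1,500 runs, with 80% wear in Intervention and none in Control (assumed). The gain over endline-only is about 4.5%, 13% and 28.5% both with and without adherence. Adherence inflates the variance of the treatment effect about threefold in both models, so the ratio between them does not move.

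**When the gain vanishes.** At n = 364 the p<0.20 screen corresponds to t = 1.284 on 362 df. The threshold is |r| = 1.284/√(362 + 1.284²) = 0.067. A score just at that threshold would narrow the CI by only 0.2%. By Fisher's z, the probability of passing is about 73% at r = 0.1 and 99.5% at r = 0.2. At every r in the table, a score that is offered to the screen is therefore practically certain to enter.

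**The case against.** The strongest objection is that the loss may never occur. At any correlation large enough to matter, the baseline score passes the screen once it is offered, and an analyst would naturally offer it. This largely stands: the percentages describe what happens if the score is not offered, and the expected loss is smaller. It does not remove the point. The SAP names no candidates, and the screen is introduced for potential determinants, so it may not govern the treatment comparison at all.

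A reader might infer that endline versus change score is wholly open. SAP 4.6.2 weakens that inference: it speaks of change for skill grade and for attitude but not for visual function, and 9.1 defines a score rather than a difference. The endline score is the likelier reading, so the change-score figures are secondary. This remains an inference, because no sentence settles it.

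A reader might also infer bias, or a weakness in the primary analysis. The documents support neither on this ground. Randomisation protects the comparison with or without the baseline score, and the efficiency model already contains baseline efficiency.

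Finally, the upper values of r have no support in the text. Glasses correct near vision in one arm, so a weak correlation there is plausible (an assumption too). At 0.3 the gain over endline-only is only about 3% to 5%.

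**Conclusion.** The gap is real but minor, and closing it is an optional improvement to one secondary outcome. SAP 9.1 fixes age, tenure, baseline efficiency and adherence for APEDS, and does not fix the baseline APEDS score. Against an endline model without that score, fixing it narrows the interval by about 5%, 13% or 29% at an assumed residual r of 0.3, 0.5 or 0.7. There is essentially no gain if the score would have been offered to the screen and passed. If a change score were used instead, the gain would be about 19%, 13% or 8% with equal SDs. These sizes rest on assumed correlations, because the documents give none for APEDS. What the edit secures in every case is a covariate list settled before the data are seen.

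**What to change.** Add to SAP 9.1:

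> The endline APEDS VFQ score will be compared between arms by ANCOVA with the baseline APEDS VFQ score and the stratification factors (age, tenure, baseline efficiency) as fixed covariates; the p<0.20 screen will not be used to choose covariates for this comparison.

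Two matters belong in the same edit:

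- **Adherence.** Reconcile this list with the sentence that makes adherence a covariate for secondary outcomes, so that 9.1 does not give two lists for APEDS. Whether adherence belongs in the model is a separate issue.
- **Missing baseline scores.** The imputation in 9.1 is described for primary outcomes only. State that participants without a baseline APEDS score stay in the model, for example by mean imputation of that baseline covariate. Otherwise the new covariate would drop them.

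The cost is SAP wording and one extra covariate in one secondary model. No visits, data items or participants are added.

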### **7. ANALYSIS POPULATIONS**

## 7.1 Primary analysis strategy

All outcomes will be assessed by Intention To Treat: participants will be analysed in the groups into which they were randomly allocated, i.e. comparing the outcomes of all workers allocated to the Intervention Group with workers allocated to the Control Group, regardless of allocation received.

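### The primary ANCOVA adjusts for spectacle wear observed after randomisation, so the treatment effect that carries inference is not the intention-to-treat effect

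*SAP*

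**What the plan says.** - **Analysis strategy.** SAP Section 7.1: "All outcomes will be assessed by Intention To Treat", with workers kept in their allocated groups.
- **Model table.** The ANCOVA table in SAP Section 9.1 is headed "Factors and covariates at baseline". One of its rows is "Spectacle wear compliance", a factor split at the median. All terms enter as additive main effects.
- **Text after the table.** The same section adds that "Adherence to wearing glasses will be considered a covariate in the regression models assessing primary and secondary outcomes". The stated reason is to "account for any potential confounding effect on the productivity measures".
- **Which result counts.** Crude and adjusted estimates will both be shown, but "the primary inference will be based on the adjusted analysis".
- **When wear is measured.** SAP Section 4.10.2 lists the form "Spectacle Wear Compliance (on a weekly basis over the 3-month intervention period". Section 6 describes covert daily observation at work.
- **Other uses of wear.** Section 4.6.2 makes adherence a secondary outcome. Section 9.2 lists a compliance subgroup with the same median split.

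The combined protocol and SAP has the same row in its Section 9.1 table but not the two sentences on adherence adjustment. The SAP therefore goes further than that document.

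**The concern.** Workers in the intervention arm receive their trial glasses because of allocation, and wear is recorded afterwards. Wear is therefore not a baseline variable, whatever the table heading says. Nor can it confound the randomised comparison, because it follows allocation. It is the mechanism under test.

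Conditioning on it does two things. It removes from the arm coefficient the part of the effect that runs through wear. It also lets in bias if workers who wear their glasses differ in unmeasured efficiency from those who do not.

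The SAP does not say whose median defines the split, how control workers are coded, or whether the covariate in the text is the same term as the two-level factor in the table. Two analysts following the plan could reach opposite conclusions from the same data, and the choice could be made after the data are seen. Read literally, the plan also adjusts the secondary outcome of adherence for adherence.

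**Working it through.** **1. The plan's own sample size.** Section 4.8 gives a difference of 0.0425, SD 0.19, correlation 0.8, two-sided 5% and 90% power.

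n = 2 × ((1.96 + 1.2816) × 0.19 / 0.0425)² × (1 − 0.8²) = 420.0 × 0.36 = 151.2, rounded up to the stated 152 per group. The figure holds only with baseline efficiency in the model; without it, 420 per group are needed.

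**2. Precision with and without baseline efficiency.** Three months of 10% loss leave 250 × 0.9³ = 182 per arm. At 80% wear, an effect proportional to wear is 0.8 × 0.0425 = 0.034.

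- With baseline: SE = √(2 × 0.19² × 0.36 / 182) = 0.0120; power for 0.034 is 81%.
- Crude: SE = √(2 × 0.19² / 182) = 0.0199; power is 40%.

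**3. Simulation model.** Efficiency = 0.53 + 0.8 × (baseline − 0.53) + 0.0425 × wear + residual, with residual SD 0.19 × √0.36 = 0.114. Each worker contributes one mean; there are 182 workers per arm and 2,000 replicates.

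Assumptions not in the documents: wear among wearers follows Beta(3.2, 0.8), mean 0.80; 0%, 10% or 40% of controls wear glasses (Section 5.2.2 allows outside purchase but gives no rate); glasses act only through wear. Each model has arm and baseline efficiency, plus the wear term shown.

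**4. Real effect, wear unrelated to unmeasured efficiency.** Arm coefficient, with power in brackets:

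| Wear term | 0% control wear | 10% | 40% |
|---|---|---|---|
| None | 0.034 (80%) | 0.031 (72%) | 0.020 (39%) |
| Continuous | about 0 | about 0 | about 0 |
| Intervention-arm median | 0.028 (48%) | 0.024 (39%) | 0.015 (21%) |
| Pooled median | not estimable | 0.009 (8%) | 0.010 (13%) |
| Each arm's own median | 0.040 (79%) | 0.037 (70%) | – |

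- Continuous wear has SE 0.040, 0.024 and 0.015 and rejects in 5–6% of runs.
- With no control wear, the pooled-median factor is identical to arm. If 10% of the intervention arm also never wear glasses, the pooled median is 0, the factor drops out and nothing changes (0.030, 72%).

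**5. No true effect, 10% control wear, wear correlated with the efficiency residual.**

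| Correlation | Continuous | Pooled median | Intervention-arm median |
|---|---|---|---|
| −0.15, false superiority | 20% | 9% | 12% |
| −0.3, false superiority | 56% (estimate +0.050) | 31% | 36% |

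At +0.3, continuous wear gives false harm in 57% of runs (estimate −0.050), while each arm's own median gives false superiority in 46%. Without a wear term, two-sided rejection stays at 5–6%.

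**6. Sensitivity to the wear model.** A separate simulation with Beta(4, 1) wear and a correlation of −0.3 gave false superiority of 28% (continuous), 18% (pooled median) and 20% (intervention-arm median) at 10% control wear. With no control wear, two-sided rejection for continuous wear was about 74%. The pattern is stable; the exact rates are not.

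**The case against.** - **Allocation is respected in form.** Workers are analysed in their randomised groups. This is true, and the charge is narrower: the arm coefficient stops estimating the intention-to-treat effect.
- **The crude estimate is also reported.** It does not carry inference, and it leaves out the baseline efficiency on which the sample size depends.
- **The row could mean factory-level compliance.** A factory-level term did no harm in simulation (0.034, 80% power). But only the Section 9.2 subgroup mentions the factory; Section 6 and the text of Section 9.1 describe wearing of glasses by workers. A plan that is sound only on an unstated reading still needs correcting.
- **The SAP gives some coding.** It does: a median split. The population for the median, the coding of controls and the form of the covariate in the text are missing.
- **The figures rest on assumptions.** This stands. The correlations of −0.3 to +0.3 have no source in the documents, and with no effect and no such correlation the type I error stays near 5%. The zero estimate under continuous wear follows from assuming that glasses act only through wear. The SAP models daily efficiency with participant-clustered errors, so one mean per worker is a simplification.
- **The p < 0.20 rule belongs to a separate analysis of determinants.** Possibly. The SAP does not say that "all significant variables with p values less than 0.20 in simple regression analyses will be included in multiple regression models" leaves the primary model untouched, so this is a secondary risk.

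None of these removes the contradiction between Sections 7.1 and 9.1.

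**Conclusion.** The concern holds and needs correction before the outcome data are analysed by arm. It follows from the text alone: a variable observed after allocation, on the causal path, sits in the model that supports the superiority claim.

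The magnitudes are illustrative. Under the stated assumptions the error has no fixed direction: a real effect of 0.034 can disappear, shrink, rise to 0.040, stay unchanged or become inestimable. The adjustment therefore cannot be defended as conservative. False superiority or false harm arises only if wear is related to unmeasured efficiency. The SAP gives no ground for ruling that out, and its own reference to confounding suggests that it expects some such relation.

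**What to change.** 1. Delete the wear-compliance row from the SAP Section 9.1 table, and the matching row in the combined protocol and SAP if that document is still in force.
2. Delete the two SAP sentences on adherence adjustment, for primary and secondary outcomes alike.
3. Add: *No variable measured after randomisation, in particular spectacle wear or adherence, will enter the primary or secondary outcome models, including through the p < 0.20 selection rule.* If day-level terms such as calendar date are wanted for the daily outcome, name them as exceptions.
4. Base primary inference on the intention-to-treat ANCOVA with arm, baseline efficiency, age, tenure, sex, skill grade and factory type.
5. If an effect of actual wear is wanted, make it supplementary, for example a complier-average analysis with randomised arm as the instrument. State that it assumes allocation acts only through wear, which is uncertain in a trial where participants are not masked and Section 4.5 itself raises placebo effects.
6. In Section 9.2, say whether the compliance subgroup is factory-level or individual-level. If individual-level, do not analyse it as a subgroup of the randomised comparison.

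The cost is SAP wording and, at most, one optional supplementary analysis. No new data are needed.
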